14.4 Electrocardiogram (ECG)

ECG is performed at Baseline, Weeks 2, 4, 8, 12, 16, 28, 40, and Week 52/ET.

All tracings will be evaluated by a central reading laboratory, including any collected outside of the clinic due to COVID-19 disruptions when possible.. At the Baseline visit the

machine-read results will also be recorded. ECG data summaries, including the cardiologist's interpretation, will be analyzed using the centrally evaluated data.

14.4.1 ECG Variables

ECG variables include heart rate, PR interval, RR interval, QRS interval, QT interval, and QTc intervals. QTc intervals include QTcB (Bazett's formula) and QTcF (Fridericia's formula). QTcF will also be categorized into the following categories (msec):

- Observed: ≤ 450 , 451 to 480, 481 to 500, and >500
- Change from Baseline: ≤ 10 , 11 to 30, 31 to 60, and >60

14.4.2 ECG Methods of Analysis

14.4.2.1 Observed Values and Change from Baseline

Observed values and the changes from Baseline of ECG variables will be summarized using descriptive statistics at Baseline and all scheduled post-Baseline visits. For the QTcF categorical analysis, the number and percentage of subject in each category will be summarized at each scheduled visit as well as overall post-Baseline maximum (only for the OL study period).

14.4.2.2 PCI Values

Electrocardiogram values will be considered PCI if they meet or exceed the upper limit values listed in Table 8. The number and percentage of subjects with PCI values will be summarized at scheduled post-Baseline visits and for overall post-Baseline (only for the OL study period). For the by-visit summary, the numerator for the percentage is the number of subjects with a post-Baseline PCI value for the given parameter, visit and cohort, and the denominator is the number of subjects with non-missing values for the given parameter, visit and cohort. For the overall post-Baseline summary, the numerator for the percentage is the number of subjects with at least 1 post-Baseline PCI value for the given parameter and cohort, and the denominator is the number of subjects with at least 1 post-Baseline value for the given parameter and cohort.

Table 8 Criteria for Potentially Clinically Important ECG Values

ECG Parameter	Unit	High PCI Criteria
QRS Interval	msec	≥ 120
PR Interval	msec	≥ 220
QTcB or QTcF	msec	>500
QTcB or QTcF: change from baseline	msec	>60

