4.3 Exclusion Criteria

A subject must meet none of the following exclusion criteria to be eligible for the study:

1. Subject is judged by the Investigator or the Medical Monitor to be inappropriate for the study, due to AEs, medical condition, or noncompliance with investigational product or study procedures in the antecedent study, or is judged to be a danger to self or others
2. Is in hospice, is receiving end-of-life palliative care, or has become bedridden
3. Has any of the following ECG results at the EOT/ET visit of the antecedent study:
 - a. If the subject is **not** on citalopram, escitalopram, or venlafaxine:
 - i. QTcF >450 ms, if QRS duration <120 ms
 - ii. QTcF >470 ms, if QRS duration \geq 120 ms
 - b. If the subject is on citalopram, escitalopram, or venlafaxine:
 - i. QTcF >425 ms, if QRS duration <120 ms
 - ii. QTcF >450 ms, if QRS duration \geq 120 ms
4. Has a heart rate <50 beats per minute. If bradycardia is secondary to iatrogenic or treatable causes and these causes are treated, a heart rate assessment can be repeated at the EOT/ET visit of the antecedent study.
5. Has a body mass index (BMI) <18.5 kg/m² or known unintentional clinically significant weight loss (i.e., \geq 7% of body weight) over past 6 months
6. Has clinically significant laboratory abnormalities in the antecedent study that, in the judgment of the Investigator or Medical Monitor, would either:
 - a. jeopardize the safe participation of the subject in the study; OR
 - b. would interfere with the conduct or interpretation of safety or efficacy evaluations in the study
7. Is suicidal as defined below at Visit 1 (Baseline) of the ACP-103-047 study:
 - a. If the subject was assessed in the antecedent study using the Columbia-Suicide Severity Rating Scale (C-SSRS), he or she must not be actively suicidal at Visit 1 (Baseline) (including an answer of “yes” to C-SSRS questions 4 or 5) and must not have attempted suicide (using the “Since Last Visit” version) prior to Visit 1 (Baseline) of the present study; OR
 - b. If the subject is not able to reliably complete the C-SSRS in the Investigator’s judgment or if the Global Clinician Assessment of Suicidality (GCAS) scale was used in the antecedent study, the subject must not be suicidal as assessed by the GCAS score (i.e., a score of 3 or 4) based on Investigator’s assessment of behavior since-last-visit at Visit 1 (Baseline); OR

- c. The subject is actively suicidal in the Investigator's judgment

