14.2.5.3 Potentially Clinically Important Laboratory Values

The number and percentage of subjects with potentially clinically important (PCI) laboratory values at scheduled post-Baseline visits and overall post-Baseline will be summarized by Baseline status (all or within normal range) for selected parameters. PCI criteria are listed in [Table 5](#) and [Table 6](#). Subjects with multiple PCI values for a given parameter will be counted only once for that parameter. All post-Baseline values will be considered, including unscheduled and out of window values. PCI tables will be presented for OL timepoints only using OL Baseline, and DB+OL timepoints using the DB Baseline from the antecedent study (see [Section 5.2](#) and [Table 4](#)).

For the by-visit summary, the numerator for the percentage is the number of subjects with a post-Baseline PCI value for the given parameter, visit, and cohort, and the denominator is the number of subjects with non-missing values for the given parameter, visit, and cohort. For the overall post-Baseline summary, the numerator for the percentage is the number of subjects with at least 1 post-Baseline PCI value for the given parameter and cohort, and the denominator is the number of subjects with at least 1 post-Baseline value for the given parameter and cohort. For hemoglobin, hematocrit and uric acid, the count and percentage of subjects with PCI values will be presented for each gender as well as for both genders combined. A listing of all PCI values in study ACP-103-047 will be provided. This listing will include all observations from study ACP-103-047 for those subjects and parameters for which at least one PCI value (including OL Baseline) was observed.

Table 5 Criteria for Potentially Clinically Important Laboratory Values – Hematology and Chemistry

Analyte	Conventional Unit	Low PCI Criteria	High PCI Criteria	SI Unit	Low PCI Criteria	High PCI Criteria
Hematology (whole blood)						
Hemoglobin (male)	g/dL	<11	>18	g/L	<110	>180
Hemoglobin (female)	g/dL	<10	>17	g/L	<100	>170
Hematocrit (male)	%	<30	>55	L/L	<0.3	>0.55
Hematocrit (female)	%	<30	>50	L/L	<0.3	>0.5
Leukocyte (White Blood Cell Count)	x 10 ³ /uL	≤2.8	≥15	x 10 ⁹ /L	≤2.8	≥15
Neutrophils	x 10 ³ /uL	≤1.5	No upper limit	x 10 ⁹ /L	≤1.5	No upper limit
Platelet Count	x 10 ³ /uL	≤75	≥700	10 ⁹ /L	≤75	≥700
Chemistry (serum or plasma)						
ALT (SGPT)	U/L	No lower limit	≥3 X ULN	U/L	No lower limit	≥3 X ULN

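### The QRS and PR rows of the ECG PCI table count subjects already at or above the limit at Baseline, so new findings cannot be told from pre-existing ones

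*SAP*

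**What the plan says.** SAP 14.4.2.2 plans this ECG summary: "The number and percentage of subjects with PCI values will be summarized at scheduled post-Baseline visits and for overall post-Baseline". Table 8 decides what counts as PCI: "Electrocardiogram values will be considered PCI if they meet or exceed the upper limit values listed in Table 8". It lists QRS of at least 120 msec, PR of at least 220 msec, QTcB or QTcF above 500 msec, and a QTcB or QTcF change from Baseline above 60 msec. Only the last is relative to Baseline.

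In the overall row, "the numerator for the percentage is the number of subjects with at least 1 post-Baseline PCI value for the given parameter and cohort". Everyone with an ECG result after Baseline forms the base of that percentage: "the denominator is the number of subjects with at least 1 post-Baseline value for the given parameter and cohort". The by-visit rule has the same form. Neither mentions the Baseline value.

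Protocol 4.3, exclusion criterion 3, uses QRS only to choose which QTcF ceiling applies. For subjects not on the three named antidepressants, the wide-QRS exclusion begins "QTcF >470 ms, if QRS duration" and applies from 120 ms upward. A second pair of ceilings applies under the condition "If the subject is on citalopram, escitalopram, or venlafaxine", again with a separate one for QRS of 120 ms or more. QRS is not itself a reason for exclusion. Appendix A, on restricted antimicrobials, also provides for subjects whose Baseline QRS is 120 ms or more. No entry criterion sets a limit on PR.

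**The concern.** The QRS value at which the protocol switches to a wider QTcF ceiling, 120 ms, is also the value at which the SAP declares QRS potentially clinically important. Subjects at or above the PCI limit are thus admitted by design. PR has the same gap because entry does not restrict it.

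Both cohorts take open-label pimavanserin, so there is no concurrent untreated group from which to read the background frequency of conduction delay. Each subject's own Baseline is the main reference. A count that ignores it cannot say how many subjects crossed the limit during the study, which is the question that a long-term safety table is expected to answer.

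The SAP treats its other PCI analyses differently. Laboratory PCI counts "will be summarized by Baseline status (all or within normal range) for selected parameters". Blood pressure and pulse PCI (Table 7) need an extreme value and a change from Baseline together, and weight PCI is a percentage change. The documents give no reason for handling QRS and PR otherwise.

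**Working it through.** The plan states no figure here that could be reproduced. The check sets the rules side by side and then illustrates the possible size.

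**Step 1. Which Table 8 rows can an unchanged entrant meet?**

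| Table 8 row | Entry rule (Protocol 4.3) | Counted with no change? |
|---|---|---|
| QRS ≥120 msec | Admitted; QRS only selects the QTcF ceiling | Yes |
| PR ≥220 msec | No limit | Yes |
| QTcF >500 msec | Ceiling of 425, 450 or 470 ms, depending on QRS and antidepressant | Practically no |
| QTcB >500 msec | No limit on QTcB | Possible; the documents give no basis for sizing it |
| QTc change >60 msec | Not applicable; relative to Baseline | No |

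**Step 2. One subject followed through.** Take a subject with Baseline QRS of 130 ms and QTcF of 470 ms or less, not on citalopram, escitalopram or venlafaxine. Criterion 3 does not exclude this subject. If QRS stays at 130 ms, the change from Baseline is 0 at each of the eight post-Baseline visits (Weeks 2, 4, 8, 12, 16, 28, 40 and 52). The subject is still in the QRS PCI numerator at all eight visits and in the overall row.

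**Step 3. Do other outputs count new onset?**
- SAP 14.4.2.1 summarizes observed values and changes for all ECG variables. These are distribution summaries and do not count subjects crossing a limit.
- SAP 14.4.2.3 gives a shift table of the cardiologist's overall reading, normal or abnormal. It is not by parameter, and a subject already abnormal at Baseline cannot show a new QRS or PR finding in it.
- SAP 14.4.2.4 lists all study observations for any subject and parameter with a PCI value, Baseline included. New cases can be separated there, but only by hand.

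**Step 4. Illustration for QRS.** None of these inputs is in the documents; all are assumptions:
- b, the share entering with QRS ≥120 ms: 2% to 15%
- r, the share of those with at least one post-Baseline value ≥120 ms: 0.9 to 1.0
- i, new onset among the rest: 1% to 2%

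Planned overall PCI rate = b × r + (1 − b) × i.

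Share pre-existing = (b × r) / (planned rate).

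The rate restricted to subjects below the limit at Baseline is i.

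| b | Planned rate, i = 1% | Pre-existing | Planned rate, i = 2% | Pre-existing |
|---|---|---|---|---|
| 2% | 2.78–2.98% | 65–67% | 3.76–3.96% | 48–51% |
| 5% | 5.45–5.95% | 83–84% | 6.40–6.90% | 70–72% |
| 10% | 9.90–10.90% | 91–92% | 10.80–11.80% | 83–85% |
| 15% | 14.35–15.85% | 94–95% | 15.20–16.70% | 89–90% |

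Lower extreme: b = 0.02, r = 0.9, i = 0.02 gives 0.018 + 0.0196 = 0.0376, and 0.018 / 0.0376 = 48%.

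Upper extreme: b = 0.15, r = 1.0, i = 0.01 gives 0.15 + 0.0085 = 0.1585, and 0.15 / 0.1585 = 95%.

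In subjects, with the planned 750 all having a post-Baseline ECG, b = 5%, r = 1.0 and i = 1%: 37.5 pre-existing plus 712.5 × 0.01 = 7.1 new, about 45 in all. The restricted row would show about 7 of 712.

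The same formula applies to PR, but no PR figures are offered because there is nothing in the documents to anchor a range.

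**The case against.** The strongest reply is that Baseline is not ignored in the ECG section as a whole. Change from Baseline is summarized for every ECG variable, against both the OL and the DB Baseline, and a subject who stays at 130 ms contributes zero. The listing lets a reviewer separate old from new cases. A conduction disorder reported as an adverse event is treatment-emergent under SAP 14.1 only if it began on or after the first OL dose. The SAP calls these PCI values post-Baseline, not new or treatment-emergent, and the study is descriptive with no hypothesis tests. All of this stands and keeps the point modest. It does not supply the missing count: no table gives the number of subjects with new QRS or PR values at or above the limit.

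A reader might also infer that all ECG PCI rows, QTc included, share the defect. The documents do not support that. The 60 msec row is already a change criterion, and QTcF change bands are tabulated. Entry QTcF is capped at 470 ms or lower, so new-onset rows for QTcF above 480 or 500 ms would nearly duplicate the existing ones. For the observed QTcF bands ("451 to 480, 481 to 500, and >500", after a first band of 450 or less), overlap is confined to wide-QRS subjects not on the three antidepressants who enter at 451 to 470 ms. Band counts are shown at each scheduled visit, so the Baseline distribution is visible. The QTcF limits and QT drug restrictions show concern about QT, so they cannot be used to argue that QRS or PR is a core question here.

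**Conclusion.** The point holds for the QRS and PR rows. As written, each counts everyone at or above the limit after Baseline, including subjects who entered there and did not change, and no other table isolates new onset. This follows from the text and needs no assumed number.

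Its size cannot be taken from the documents. Under the assumed ranges above, between about half (48%) and 95% of counted QRS subjects would be pre-existing. A reader might go further and infer that these rows mainly reproduce Baseline prevalence, that a real effect would be hidden, or that chronic conduction delay would be taken for a drug effect. That is not established: the low end of the range is just under half, every input is assumed, and the change summaries and the listing would show Baseline context. The supported conclusion is that the two rows are hard to interpret on their own and that the SAP's own laboratory rule would cure this.

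**What to change.** In SAP 14.4.2.2, present QRS and PR PCI counts by Baseline status, following 14.2.5.3:

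- (a) all subjects, as now;
- (b) subjects below the PCI limit at OL Baseline, with those subjects (having at least one post-Baseline value, or a value at the given visit) as the denominator.

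The Baseline must be named, because SAP 5.2 uses two. For Cohort 2 (DB pimavanserin), also present (b) against the DB Baseline. The OL Baseline in that cohort is already on drug, and restricting on it alone would drop subjects who first crossed the limit during double-blind treatment.

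Optionally, cross-classify the QTcF 451 to 480 band by Baseline band. Added rows for QTcF above 480 or 500 ms are not needed.

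The cost is a short SAP addition and a few table rows from data already collected. Row (b) has a slightly smaller denominator; row (a) is unchanged.

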14.4.2.3 Cardiologist Interpretations

For cardiologist's interpretations, the number and percentage of subjects with ECG results that are classified as normal or abnormal will be summarized at scheduled visits. The overall post-baseline worst interpretation (i.e. if a subject has one or more ECG results that are considered as abnormal, this subject will be counted in the abnormal category) will also be summarized (only for the OL study period). Cardiologist's interpretations will also be summarized in a shift table to determine the number and percentage of subjects with ECG results classified as normal or abnormal at scheduled post-Baseline visits relative to the same classification at the Baseline visit. The shifts from Baseline to overall post-Baseline worst interpretation (only for the OL study period) will also be presented. For the by-visit shift summary, the denominator is the number of subjects with non-missing cardiologist's interpretation at Baseline and the given visit for the given cohort. For the summaries of shift from Baseline to the overall post-Baseline worst interpretation, the denominator is the number of subjects with non-missing Baseline and at least 1 post-Baseline cardiologist's interpretation for the given cohort.

14.4.2.4 Data Listings

All data, including machine-read Baseline results, will be listed. A listing of all ECG PCI values in study ACP-103-047 will be provided. This listing will include all observations from study ACP-103-047 for those subjects and parameters for which at least one PCI value (including Baseline) was observed.

14.5 Physical Examination

Physical examination is performed at Baseline, Week 28, and Week 52/ET visits.

Physical examination results (normal, abnormal, and not done) at Baseline, Week 28, and Week 52/ET will be summarized in a frequency table by cohort and body system.

14.6 Other Safety Variables

14.6.1 ESRS-A

The ESRS-A is assessed at Baseline, Weeks 2, 4, 8, 12, 16, 28, 40, and Week 52/ET visits.

The ESRS-A total score and the 4 individual global CGI-S scores will be summarized using descriptive statistics at Baseline and scheduled post-Baseline visits. The change from Baseline scores will also be summarized at scheduled post-Baseline visits. For each of the above endpoints, results will be presented for OL timepoints only using OL Baseline, and DB+OL timepoints using the DB Baseline from the antecedent study (see [Section 5.2](#) and [Table 4](#)).

The individual item scores and subscale scores will be listed but not summarized.

14.6.2 MMSE

The MMSE is assessed at Baseline, Weeks 2, 4, 8, 12, 16, 28, 40 and Week 52/ET visits.

The MMSE total score will be summarized using descriptive statistics at Baseline and scheduled post-Baseline visits. The change from Baseline scores will also be summarized at scheduled post-Baseline visits. The MMSE total score will be presented for OL timepoints only using OL Baseline, and DB+OL timepoints using the DB Baseline from the antecedent study (see [Section 5.2](#) and [Table 4](#)).

The individual item scores will be listed but not summarized.

14.6.3 Suicidality

The C-SSRS will be administered if the subject, in the Investigator's judgement, is able to reliably complete it. Otherwise, the GCAS will be administered and used thereafter in the study.

14.6.3.1 C-SSRS

The C-SSRS is assessed (when applicable) at Baseline, Weeks 2, 4, 8, 12, 16, 28, 40 and Week 52/ET visits.

The event counts and the number and percentage of subjects reporting any post-OL Baseline suicidal ideation (wish to be dead; non-specific active suicidal thoughts; active suicidal ideation with any methods (not plan) without intent to act; active suicidal ideation with some intent to act, without specific plan; active suicidal ideation with specific plan and intent), suicidal behavior (preparatory acts or behavior; aborted attempt; interrupted attempt; actual attempt; suicide), or suicidality (any suicidal ideation or behavior) will be tabulated.

The event counts and the number and percentage of subjects reporting any post-OL Baseline non-suicidal self-injurious behavior will also be tabulated.

For calculating the percentages, the denominator will be the number of subjects with an OL C-SSRS assessment within each cohort. The above summaries will be presented only for the OL study period.

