5.3.4 C-SSRS

The C-SSRS is assessed (when applicable) at Baseline, Weeks 2, 4, 8, 12, 16, 28, 40 and Week 52/ET visits.

The Columbia-Suicide Severity Rating Scale (C-SSRS) will be used to assess suicidal ideations and behaviors in subjects who are able to complete the assessment (subjects without dementia, defined as an $MMSE \geq 25$), and subjects with dementia who the Investigator has determined can complete the C-SSRS. The C-SSRS monitors changes in suicidal thinking and behavior over time, in order to determine risk. Four constructs are measured: the severity of ideation, the intensity of ideation, behavior, and lethality.

The C-SSRS version assessing information since the last visit will be completed at all visits (including the Baseline visit). The C-SSRS results for each subject should be reviewed by the Investigator at each visit. If at any time the C-SSRS results for a given subject reveal potential suicidality, then the Investigator should assess the clinical significance of such results. If a clinically significant risk of suicidality is identified for a subject, then the Investigator should discontinue the subject and implement appropriate treatment.

There are 5 questions about suicidal ideation, representing 5 types of suicidal ideation: wish to be dead; non-specific active suicidal thoughts; active suicidal ideation with any methods (not plan) without intent to act; active suicidal ideation with some intent to act, without specific plan; active suicidal ideation with specific plan and intent. If a subject answers “yes” to any of these 5 questions, this subject will be counted as having suicidal ideation.

There are 5 questions about suicidal behavior, representing 5 types of suicidal behavior: preparatory acts or behavior; aborted attempt; interrupted attempt; actual attempt; suicide. If a subject answers “yes” to any of these 5 questions, this subject will be counted as having suicidal behavior.

Missing C-SSRS item scores will not be imputed.

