8.2 Disease Characteristics and Neuropsychiatric History

Disease characteristics at OL Baseline will be summarized using descriptive statistics. MMSE total score, CGI-S, EQ-5D-5L VAS, SDI total score, and ESRS-A total score will be presented as continuous variables. In addition, CGI-S will be presented as a categorical

variable using categories of 1 to 7, and MMSE will be presented as a categorical variable using categories of ≤ 10 , 11 to 17, 18 to 24, and 25 to 30. For the C-SSRS the number and percentage of subjects having suicidal ideation or behavior since the last visit will be presented. For the GCAS, the number and percentage of subjects within each rating since the last visit (absent, feels life is not worth living, wishes he/she were dead or any thoughts of possible death to self, suicidal ideas or gestures, and attempts at suicide) will be presented.

Neuropsychiatric history will be summarized descriptively for continuous and categorical variables. The OL Baseline visit date will be used as the reference date for calculation of durations. For both the Disease Characteristics and Neuropsychiatric History, summaries by region (North America, Europe, and rest of world) will also be presented. The Neuropsychiatric history will be pushed into the -047 database from the -046 study. If there have been any changes in the subject's neuropsychiatric history since completing this form for the -046 study, appropriate updates should be made by editing the affected fields.

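### The C-SSRS and GCAS tables do not separate new or worsened suicidality from ideation already present at OL Baseline (minor)

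*SAP*

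**What the plan says.** **The table.** SAP 14.6.3.1 counts "the number and percentage of subjects reporting any post-OL Baseline suicidal ideation (wish to be dead; non-specific active suicidal thoughts" and the remaining ideation types, five types of behavior, any suicidality, and non-suicidal self-injury. For percentages, "the denominator will be the number of subjects with an OL C-SSRS assessment within each cohort". On period, "The above summaries will be presented only for the OL study period". Under SAP 5.3.4, after a yes to any one of the five ideation questions, "this subject will be counted as having suicidal ideation".

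**The entry rule.** Under Protocol 4.3, criterion 7a, a subject assessed with the C-SSRS "must not be actively suicidal at Visit 1 (Baseline) (including an answer of “yes” to C-SSRS questions 4 or 5". An earlier suicide attempt is also a bar under 7a. Criterion 7b bars GCAS ratings of 3 or 4. Criterion 7c, which begins "The subject is actively suicidal in the", adds the Investigator's judgment.

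**The baseline summary.** SAP 8.2 states: "For the C-SSRS the number and percentage of subjects having suicidal ideation or behavior since the last visit will be presented". The GCAS rating at OL Baseline is summarized in the same way.

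**The GCAS table.** SAP 14.6.3.2 gives the worst rating after OL Baseline and the number with a rating of 3 or 4, for the open-label period, from the clinician rating.

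**The concern.** Suicidality is the first exploratory safety objective in both documents, and Protocol 1.4 lists depression/dysphoria among the symptoms of the subjects to be enrolled. A safety reader will want to know how many subjects developed ideation, or moved to a more serious level, after starting open-label drug. The planned tables answer a different question: how many reported any ideation after OL Baseline, whatever they reported before. If some subjects enter with a passive wish to be dead and keep reporting it, they are added to the new cases and cannot be told apart in the table.

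Two separate totals, one at OL Baseline and one afterwards, do not repair this. The same pair of totals can arise from full persistence with no new cases, or from full resolution with an equal number of new cases.

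**Working it through.** The documents state no rate of ideation, before or after OL Baseline, and the study has no power basis or hypothesis test. There is therefore no planned figure to reproduce. The check is a reading of the definitions, followed by an illustration.

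**Step 1: can a subject enter with ideation?** Criterion 7a names questions 4 and 5 and a suicide attempt; 7c covers active suicidality. Neither reaches a passive wish to be dead (question 1). Questions 2 and 3 are not named but could be excluded by judgment under 7a or 7c. On the GCAS, 7b leaves ratings 1 and 2 admissible. So question 1 and GCAS 1–2 are clearly admitted, and questions 2–3 possibly.

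**Step 2: does the table use entry status?** The numerator is any later yes. The denominator is everyone with an open-label C-SSRS rating. There is no baseline stratum, shift or new-onset row.

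**Step 3: what exactly is counted?** SAP 5.3.4 requires the since-last-visit version at every visit, Baseline included. A later yes therefore refers to an interval after the Baseline visit, and ideation that ended before then is not counted. The first interval includes the short gap before the first dose on the next day.

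**Step 4: how are other safety data treated in the SAP?**

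| Measure | Reference |
|---|---|
| TEAEs (14.1) | Onset on or after first OL dose |
| Laboratory (14.2.5.2) | Shifts from OL and from DB Baseline |
| Blood pressure, pulse PCI (14.3.2) | Value and change from baseline both required |
| ECG interpretation (14.4.2.3) | Shift from Baseline |
| ESRS-A, MMSE (14.6.1, 14.6.2) | Change from both baselines |
| C-SSRS, GCAS (14.6.3) | None within subject |

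**Step 5: GCAS after a switch of scale.** Protocol 6.3.5.2 and SAP 5.3.5 make the first GCAS of a subject who can no longer complete the C-SSRS a lifetime and past-3-month rating. SAP 14.6.3.2 does not say that this rating is left out of the worst post-OL-Baseline rating, so suicidality from before the study could enter an open-label table.

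**Step 6: illustration, all inputs assumed.** Let b be the proportion with ideation at OL Baseline, q the chance that such a subject reports it again, and r the chance of ideation in the others.

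Table percentage = b·q + (1 − b)·r. Share already present at OL Baseline = b·q ÷ table percentage.

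Example with b = 5%, q = 0.6, r = 2%: 3.0% + 1.9% = 4.9%; share 3.0 ÷ 4.9 = 61%.

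| b | Table % (q = 0.3 to 0.9, r = 2%) | Share already present |
|---|---|---|
| 0 | 2.00 | 0% |
| 1% | 2.28 to 2.88 | 13% to 31% |
| 5% | 3.40 to 6.40 | 44% to 70% |
| 10% | 4.80 to 10.80 | 62% to 83% |

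A new-onset row restricted to subjects without ideation at OL Baseline would show 2.00% throughout. A higher r lowers the share: with b = 5%, q = 0.6 and r = 4%, it is 3.0 ÷ (3.0 + 3.8) = 44%. The table shows how the mixture behaves; it is not evidence of its size.

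**The case against.** The strongest case against is that the SAP delivers what Protocol 9.5.2 asks for: the number and percentage with ideation or behavior during the study. The endpoint is exploratory, the study is open-label and descriptive, SAP 8.2 gives the entry proportion, and SAP 5 promises listings of all data. Worsening of a prior condition may also be recorded as an adverse event (Protocol 7.2.1 and 7.3.2.1) and so reach the TEAE tables. The C-SSRS covers only subjects able to complete it, so the affected group is smaller than the study. All of this stands and limits the severity. It does not supply the split: totals do not link subjects, and listings for up to about 750 subjects over eight post-Baseline visits are no substitute for a summary.

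Three stronger readings are tempting and are not supported.

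- A reader might infer that old ideation is presented as a treatment effect. The table is labelled post-OL Baseline, never treatment-emergent, and the recall period means that what is counted was reported for an interval after the Baseline visit.
- A reader might infer that a move from passive to active ideation is hidden in one overall count. SAP 14.6.3.1 names every ideation and behavior type, and the natural reading is one row for each. The layout is left to a separate specification. Active ideation would then be visible; only the within-subject move would not.
- A reader might quote a percentage of counted subjects as pre-existing. No document gives the rates that this needs.

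**Conclusion.** The point holds in limited form. As planned, the C-SSRS and GCAS tables pool new or worsened suicidality with ideation already present at OL Baseline, while the entry rule admits question 1 and GCAS ratings 1–2, and the SAP gives the other safety measures listed above a baseline or onset reference. The conclusion rests on the wording of SAP 14.6.3.1 and 14.6.3.2 and Protocol 4.3, not on any assumed rate. Its size is unknown: nil if nobody enters with ideation, and growing with the entry proportion and with persistence. It affects how an exploratory safety table is read, and no test or sample size. Severity: minor.

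**What to change.** In SAP 14.6.3.1 and 14.6.3.2, keep the crude counts and add, by cohort:

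1. A shift table from the OL Baseline category (C-SSRS: none, ideation 1 to 5, behavior; GCAS: 0 to 4) to the worst post-OL-Baseline category.
2. The number and percentage with new or worsened suicidality, meaning a worst category above that at OL Baseline. The denominator is subjects with an OL Baseline rating and at least one later rating on the same scale.
3. A sentence leaving the lifetime/past-3-month first GCAS rating of subjects who switch scale out of the worst post-OL-Baseline rating. Listing these ratings separately keeps visible any suicidality in the interval before the switch.

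Use one reference rule in both cohorts; taking the worst of many earlier ratings in one cohort and a single pre-dose rating in the other would make the columns non-comparable. Because Cohort 2 is already on pimavanserin at OL Baseline, a second shift from DB Baseline, as for laboratory data, is worth showing for both cohorts where ACP-103-046 ratings on a comparable version exist. SAP Table 4 does not show the C-SSRS schedule in that study, so this needs checking.

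The cost is SAP wording and one table per scale, with no new data collection and no change to the entry rule. There is one downside. The OL Baseline rating covers only the interval since the last ACP-103-046 visit: about 2 weeks if the scale was rated at DB Week 6, an assumption, since 8 − 6 = 2. The later worst rating covers up to 52 weeks. Some recurrent ideation will therefore be classed as new, and a footnote should say so.
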